# 8.4.2 Method of Detecting AEs, SAEs, and Other Reportable Safety Events

Care will be taken not to introduce bias when detecting AEs and/or SAEs and other reportable safety events. Open-ended and nonleading verbal questioning of the participant is the preferred method to inquire about AE occurrence.

# 8.4.3 Follow-up of AE, SAE, and Other Reportable Safety Event Information

After the initial AE/SAE report, the investigator is required to proactively follow each participant at subsequent visits/contacts. All AEs, SAEs, and other reportable safety events, including cancer, and overdose will be followed until resolution, stabilization, until the event is otherwise explained, or the participant is lost to follow-up (as defined in Section 7.3). In

V114-029-02 FINAL PROTOCOL 16-MAR-2021

74

addition, the investigator will make every attempt to follow all nonserious AEs that occur in randomized participants for outcome. Further information on follow-up procedures is given in Appendix 3.

# 8.4.4 Regulatory Reporting Requirements for SAE

Prompt notification (within 24 hours) by the investigator to the Sponsor of SAE is essential so that legal obligations and ethical responsibilities towards the safety of participants and the safety of a study intervention under clinical investigation are met.

The Sponsor has a legal responsibility to notify both the local regulatory authority and other regulatory agencies about the safety of a study intervention under clinical investigation. The Sponsor will comply with country-specific regulatory requirements and global laws and regulations relating to safety reporting to regulatory authorities, IRB/IECs, and investigators.

Investigator safety reports must be prepared for suspected unexpected serious adverse reactions (SUSARs) according to local regulatory requirements and Sponsor policy and forwarded to investigators as necessary.

An investigator who receives an investigator safety report describing an SAE or other specific safety information (eg, summary or listing of SAE) from the Sponsor will file it along with the IB and will notify the IRB/IEC, if appropriate according to local requirements.

# 8.4.5 Pregnancy and Exposure During Breastfeeding

Information in this section is not applicable since participants are infants.

# 8.4.6 Disease-related Events and/or Disease-related Outcomes Not Qualifying as AEs or SAEs

This is not applicable to this study.

## 8.4.7 Events of Clinical Interest (ECIs)

There are no events of clinical interest for this study.

#### **8.5** Treatment of Overdose

V114-029-02 FINAL PROTOCOL

In this study, an overdose is the administration of more than 1 dose of any individual study vaccine in any 24-hour period.

No specific information is available on the treatment of overdose.

Decisions regarding dose interruptions or modifications will be made by the investigator in consultation with the Sponsor Clinical Director based on the clinical evaluation of the participant.

16-MAR-2021

75

All reports of overdose must be reported by the investigator within 5 calendar days to the Sponsor either by electronic media or paper. Electronic reporting procedures can be found in the electronic data collection (EDC) data entry guidelines. Paper reporting procedures can be found in the Investigator Trial File Binder (or equivalent).

#### 8.6 Pharmacokinetics

PK parameters will not be evaluated in this study.

# 8.7 Pharmacodynamics

Pharmacodynamic parameters will not be evaluated in this study.

#### 8.8 Biomarkers

Biomarkers are not evaluated in this study.

## 8.9 Planned Genetic Analysis Sample Collection

Planned genetic analysis samples will not be evaluated in this study.

# 8.10 Future Biomedical Research Sample Collection

If the participant's legally acceptable representative provides documented informed consent for future biomedical research, the following specimens will be obtained as part of future biomedical research:

- Buccal swab DNA for future research
- Leftover study serum at the central laboratory stored for future research after aliquoting samples for completion of immunogenicity testing

# 8.11 Medical Resource Utilization and Health Economics

Medical Resource Utilization and Health Economics are not evaluated in this study.

## 8.12 Visit Requirements

Visit requirements are outlined in Section 1.3. Specific procedure-related details are provided in Section 8.

## 8.12.1 Screening

Screening procedures will be conducted at Visit 1 as outlined in Section 1.3.

## 8.12.2 Treatment Period/Vaccination Visit

Requirements during the treatment period are outlined in Section 1.3.

If the participant develops a new clinical condition during the study that makes him/her ineligible for the study, the investigator should discuss with the Sponsor Clinical Director as soon as possible. The decision to continue the participant on study intervention requires the mutual agreement of the investigator, the Sponsor, and the participant's legally acceptable representative.

# 8.12.3 Discontinued Participants Continuing to be Monitored in the Study

A participant may discontinue from study intervention (including receipt of V114, Prevnar 13TM and concomitant vaccines provided in the study) but continue to participate in protocol-specified, AE-monitoring activities as outlined in Section 1.3, as long as the participant's legally acceptable representative does not withdraw consent. Blood draws for immunogenicity testing could occur if agreed to by the participant's legally acceptable representative at the discretion of the investigator.

## 9 STATISTICAL ANALYSIS PLAN

This section outlines the statistical analysis strategy and procedures for the study. If, after the study has begun, but prior to any unblinding, changes are made to primary and/or key secondary hypotheses, or the statistical methods related to those hypotheses, then the protocol will be amended (consistent with ICH Guideline E-9). Changes to exploratory or other non-confirmatory analyses made after the protocol has been finalized, but prior to unblinding, will be documented in a supplemental Statistical Analysis Plan and referenced in the Clinical Study Report (CSR) for the study. Post hoc exploratory analyses will be clearly identified in the CSR.

# 9.1 Statistical Analysis Plan Summary

Key elements of the statistical analysis plan are summarized below; the comprehensive plan is provided in Section 9.2 to Section 9.12.

Study Design Overview	A Phase 3, Multicenter, Randomized, Double-blind, Active-Comparator-controlled Study to Evaluate the Safety, Tolerability, and Immunogenicity of a 4-dose Regimen of V114 in Healthy Infants (PNEU-PED)
Treatment Assignment	Participants will be randomly assigned in a 1:1 ratio to V114 or Prevnar 13 TM , respectively.
Analysis Populations	Immunogenicity: Per-Protocol (PP) Safety: All Participants as Treated (APaT)

#### Primary Endpoint(s)

#### Immunogenicity:

- Anti-PnP serotype-specific IgG response rates (proportion of participants with anti-PnPs serotype-specific IgG ≥0.35 μg/mL at 30 days PD3)
- Anti-PnPs serotype-specific IgG GMCs at 30 days PD3
- Anti-PnPs serotype-specific IgG GMCs at 30 days PD4

## Safety:

- Proportion of participants with solicited injection-site AEs (swelling, redness/erythema, tenderness/pain, and hard lump/induration) from Day 1 through Day 14 following any vaccination with V114 or Prevnar 13TM
- Proportion of participants with solicited systemic AEs (irritability, drowsiness/somnolence, appetite lost/decreased appetite, and hives or welts/urticaria) from Day 1 through Day 14 following any vaccination with V114 or Prevnar 13TM
- Proportion of participants with vaccine-related SAEs from Day 1 through completion of study participation

## **Key Secondary Endpoints**

- Antigen-specific response rates for all antigens and the antigen-specific GMCs for the pertussis antigens included in PentacelTM at 30 days PD3 when administered concomitantly with V114 or Prevnar 13TM
- Anti-hepatitis A response rate at 30 days PD4 for VAQTATM when administered concomitantly with V114 or Prevnar 13TM
- Antigen-specific response rates at 30 days PD4 for all antigens included in M-M-RTMII when administered concomitantly with V114 or Prevnar 13TM
- Anti-VZV response rate at 30 days PD4 for VARIVAXTM when administered concomitantly with V114 or Prevnar 13TM
- Anti-PRP response rate at 30 days PD4 for HIBERIXTM when administered concomitantly with V114 or Prevnar 13TM
- Anti-PnPs serotype-specific IgG GMCs and IgG response rates at 30 days PD3 for the 2 unique V114 serotypes
- Anti-PnPs serotype-specific IgG GMCs at 30 days PD4 for the 2 unique V114 serotypes
- Anti-PnPs serotype 3 IgG response rates at 30 days PD3
- Anti-PnPs serotype 3 IgG GMCs at 30 days PD3
- Anti-PnPs serotype 3 IgG GMCs at 30 days PD4

## Statistical Methods for Key Immunogenicity

To address the primary immunogenicity objectives in terms of IgG response rates (H1 and H2), the between-treatment comparison will be made based on the proportion of anti-PnPs serotype-specific IgG  $\geq$ 0.35 µg/mL at 30 days PD3 for 13 shared serotypes contained in V114 and Prevnar 13TM and 2 unique serotypes contained in V114. The between-treatment difference (V114 minus Prevnar 13TM) and its 95% CI will be calculated using Miettinen and Nurminen (M&N) method [Miettinen, O. and Nurminen, M. 1985].

To address the primary immunogenicity objectives in terms of serotype-specific IgG GMCs at 30 days PD3 (H3 and H4) and 30 days PD4 (H5 and H6), the between-treatment comparison will be made based on serotype-specific IgG GMCs for 13 shared serotypes contained in V114 and Prevnar 13TM and 2 unique serotypes contained in V114. The estimation of the IgG GMC ratios and computation of the corresponding 95% CIs will be calculated using t-distribution with the variance estimate from a linear model utilizing the log-transformed antibody concentration as the response and a single term for vaccination group.

To address the secondary objectives for evaluating the concomitant vaccines, the between-group comparison will be made based on the response rate of the antigens contained in PentacelTM at 30 days PD3 and the antigens contained in VAQTATM, M-M-RTMII, VARIVAXTM, and HIBERIXTM at 30 days PD4. The betweentreatment comparison will be made based on the proportion of participants achieving the antigen-specific antibody threshold value. The between-treatment difference (V114 minus Prevnar 13TM) and the corresponding 95% CIs will be calculated using the M&N method. In addition, the between-group comparison will be made based on the antigen-specific GMCs of pertussis contained in Pentacel™ at 30 days PD3. Estimation of the GMC ratios and computation of the corresponding 95% CIs will be calculated using t-distribution with the variance estimate from a linear model utilizing the log-transformed antibody titers as the response and a single term for vaccination group. These hypothesis tests will be based on the lower bound of the 2-sided 95% CI to be greater than the prespecified margins listed in Section 9.9. To address the secondary objectives for evaluating the 2 unique V114 serotypes, between-group comparisons will be made based on the anti-PnPs serotype-specific IgG response rates and GMCs at 30 days PD3, and the anti-PnPs serotype-specific IgG GMCs at 30 days PD4, for the 2 V114 unique serotypes. Analysis of the IgG response rates will be performed using the M&N method (1985) [Miettinen, O. and Nurminen, M. 1985]. Estimation of the IgG GMC ratios and computation of the corresponding 95% CIs will be calculated using t-distribution with the variance estimate from a linear model utilizing the log-transformed antibody concentrations as the response and a single term for vaccination group. To address the secondary objectives for evaluating the superiority of serotype 3, between-group comparisons will be made based on the anti-PnPs serotype 3 IgG response rates and IgG GMCs at 30 days PD3 and IgG GMCs at 30 days PD4. Analysis of the IgG response rates will be performed using the M&N method (1985) [Miettinen, O. and Nurminen, M. 1985]. Estimation of the IgG GMC ratios and computation of the corresponding 95% CIs will be calculated using the tdistribution with the variance estimate from a linear model utilizing the logtransformed antibody concentrations as the response and a single term for vaccination group. Statistical Methods for The analysis of safety results will follow a tiered approach. P-values (Tier 1 endpoints) and 95% CIs (Tier 1 and Tier 2 endpoints) will be provided for **Key Safety Analyses** between-vaccination group differences in the percentage of participants with events; these analyses will be performed using the M&N method (1985)[Miettinen, O. and Nurminen, M. 1985]. To support the periodic review of safety and tolerability data across the V114 **Interim Analyses** Phase 3 pediatric program, an external unblinded statistician will provide unblinded interim safety summaries to an independent external Data Monitoring Committee (DMC) for their review. There are no plans to conduct an interim analysis of unblinded immunogenicity data in this study. However, unblinded immunogenicity data will be made available to the DMC upon request to enable a

Confidential

benefit-risk assessment.

#### Multiplicity

The study will be considered to have met its primary objectives if non-inferiority is demonstrated for the 13 shared serotypes and for the 2 unique serotypes for IgG GMCs and response rate at 30 days PD3 and for IgG GMCs at 30 days PD4. All hypotheses will be tested individually for each serotype at a 1-sided 0.025 alpha level. This approach controls the 1-sided type-I error rate at 0.025, thus no multiplicity adjustment is required.

The study will be considered to have met its secondary objective for a specific concomitant vaccine if non-inferiority is demonstrated for all the antigens included in that concomitant vaccine. The study will be considered to have met its secondary objective for the superiority hypotheses for the 2 unique V114 serotypes if superiority is demonstrated for the 2 unique serotypes for IgG GMCs and IgG response rates at 30 days PD3 and for IgG GMCs at 30 days PD4. The study will be considered to have met its secondary objective for the superiority hypotheses for serotype 3 if superiority is demonstrated for IgG response rates and IgG GMCs at 30 days PD3 and IgG GMCs at 30 days PD4.

No multiplicity adjustments will be made for the safety objective.

# Sample Size and Power

#### Immunogenicity:

The study will randomize participants in a 1:1 ratio to V114 or Prevnar 13TM, respectively. The overall sample size will be approximately 1720 with 860 participants into each vaccination group. The sample size was chosen to ensure sufficient power for the multiple endpoints across both primary and secondary hypotheses. With this study sample size, the overall power for all the primary hypotheses is >95%. The overall power for the secondary hypotheses for concomitant antigens evaluation is approximately 90%, and to demonstrate superiority for the 2 unique V114 serotypes is >95%. The overall power is >95% to demonstrate the superiority for the serotype 3 IgG response rates and IgG GMCs at 30 days PD3 and 94% to demonstrate the superiority for IgG GMCs at 30 days PD4. All statistical tests will be conducted at 1-sided 2.5% alpha level. Details are provided in Section 9.9.1.

#### Safety

Section 9.9.2 provides information about the ability of this study to estimate the incidence of AEs within and between the vaccination groups.

## 9.2 Responsibility for Analyses/In-house Blinding

The statistical analysis of the data obtained from this study will be the responsibility of the Clinical Biostatistics department of the Sponsor.

This study will be conducted as a double-blind study under in-house blinding procedures. The official, final database will not be unblinded until medical/scientific review has been performed, protocol deviations have been identified, and data have been declared final and complete.

The Clinical Biostatistics department will generate the randomized allocation schedule(s) for study treatment assignment. Randomization will be implemented in an IRT.

Blinding issues related to the planned interim analyses are described in Section 9.7.

# 9.3 Hypotheses/Estimation

Objectives and hypotheses of the study are stated in Section 3.

# 9.4 Analysis Endpoints

## 9.4.1 Immunogenicity Endpoints

A description of immunogenicity assessments is contained in Section 8.2.

The primary immunogenicity analysis endpoints include:

- Proportion of participants with anti-PnPs serotype-specific IgG ≥0.35 μg/mL at 30 days PD3
- Anti-PnPs serotype-specific IgG GMCs at 30 days PD3
- Anti-PnPs serotype-specific IgG GMCs at 30 days PD4

The secondary immunogenicity analysis endpoints include:

- Antigen-specific response rates for all antigens and antigen-specific GMCs for the pertussis antigens included in PentacelTM at 30 days PD3 when administered concomitantly with V114 or Prevnar 13TM
- Anti-hepatitis A response rate at 30 days PD4 for VAQTATM when administered concomitantly with V114 or Prevnar 13TM
- Antigen-specific response rates at 30 days PD4 for all antigens included in M-M-RTMII when administered concomitantly with V114 or Prevnar 13TM
- Anti-VZV response rate at 30 days PD4 for VARIVAXTM when administered concomitantly with V114 or Prevnar 13TM
- Anti-PRP response rate at 30 days PD4 for HIBERIXTM when administered concomitantly with V114 or Prevnar 13TM
- Anti-PnPs serotype-specific IgG GMCs and IgG response rates at 30 days PD3 for the 2 unique V114 serotypes
- Anti-PnPs serotype-specific IgG GMCs at 30 days PD4 for the 2 unique V114 serotypes
- Anti-PnPs serotype 3 IgG response rates at 30 days PD3
- Anti-PnPs serotype 3 IgG GMCs at 30 days PD3
- Anti-PnPs serotype 3 IgG GMCs at 30 days PD4

• Anti-PnPs serotype-specific OPA GMTs and response rates at 30 days PD3

The exploratory immunogenicity analysis endpoints include:

- Anti-PnPs serotype-specific IgG GMCs Predose4
- Anti-PnPs serotype-specific OPA GMTs and response rates Predose 4 and at 30 days PD4.
- Anti-PRP antigen response rates with an alternative threshold value at 30 days PD3 of V114 or Prevnar 13TM when administered concomitantly with PentacelTM and 30 days PD4 of V114 or Prevnar 13TM when administered concomitantly with HIBERIXTM

Table 5 summarizes the endpoints for the concomitant antigens.

Table 5 Summary of Endpoints for Concomitant Vaccine Antigens

Concomitant Vaccine	Antigen	Endpoint	Timepoint			
Secondary Endpoints for Concomitant Vaccines						
	Diphtheria toxoid	% ≥ 0.1 IU/mL	PD3			
	Tetanus toxoid	% ≥ 0.1 IU/mL	PD3			
	Pertussis – PT	% ≥ 5 EU/mL	PD3			
	Pertussis – P1	GMC	PD3			
	D . TIIA	% ≥ 5 EU/mL	PD3			
	Pertussis – FHA	GMC	PD3			
D ( ITM	D ( ' ED ( 2/2	% ≥ 20 EU/mL	PD3			
Pentacel TM	Pertussis – FIM 2/3	GMC	PD3			
	D DDM	% ≥ 5 EU/mL	PD3			
	Pertussis – PRN	GMC	PD3			
	Poliovirus 1	% with NAb>=1:8 dilution	PD3			
	Poliovirus 2	% with NAb>=1:8 dilution	PD3			
	Poliovirus 3	% with NAb>=1:8 dilution	PD3			
	Hib-PRP	$\% \ge 0.15 \ \mu g/mL$	PD3			
VAQTA TM	Hepatitis A	% ≥ 10 mIU/mL	PD4			
	Measles	% ≥ 255 mIU/mL	PD4			
M-M-R TM II	Mumps	% ≥ 10 mumps Ab units/mL	PD4			
	Rubella	% ≥ 10 IU/mL	PD4			
VARIVAXTM	VZV	% ≥ 5 gpELISA units/mL	PD4			
HIBERIX™	Hib-PRP	$\% \ge 0.15 \ \mu g/mL$	PD4			

Concomitant Vaccine	Antigen	Endpoint	Timepoint	
Exploratory Endpoints for Concomitant Vaccines				
Pentacel TM	Hib-PRP	$\% \ge 1.0 \ \mu g/mL$	PD3	
HIBERIXTM	Hib-PRP	$\% \ge 1.0 \ \mu g/mL$	PD4	

EU=endotoxin unit; FHA=filamentous hemagglutinin; FIM=fimbriae types 2 and 3; GMC=geometric mean concentrations; gpELISA= glycoprotein enzyme-linked immunosorbent assay; Hib-PRP=*Haemophilus influenzae* type b polyribosylribitol phosphate; IU=international units; mIU=milli-International Units; NAb=neutralizing antibodies; NI=non-inferiority; PD=postdose; PRN=pertactin; PT=pertussis toxin; VZV=varicella-zoster virus.

# 9.4.2 Safety Endpoints

Safety and tolerability will be assessed by clinical review of all relevant parameters including AEs and postvaccination temperature measurements following any vaccination with V114 or Prevnar 13TM.

The safety analysis endpoints include:

- Proportion of participants with solicited injection-site AEs (swelling, redness/erythema, tenderness/pain, and hard lump/induration) from Day 1 through Day 14 following any vaccination with V114 or Prevnar 13TM
- Proportion of participants with solicited systemic AEs (irritability, drowsiness/somnolence, hives or welts/urticaria, and appetite loss/decreased appetite) from Day 1 through Day 14 following any vaccination with V114 or Prevnar 13TM
- Proportions of participants with the broad AE categories consisting of any AE and a vaccine-related AE from Day 1 through Day 14 following any vaccination with V114 or Prevnar 13TM
- Proportions of participants with an SAE, a vaccine-related SAE, and discontinuation due to an AE, and death from Day 1 through 6 months following Dose 4 with V114 or Prevnar 13TM
- Participants body temperature measured Day 1 (day of vaccination) through Day 7 following any vaccination with V114 or Prevnar 13TM

16-MAR-2021

## 9.5 Analysis Populations

# 9.5.1 Immunogenicity Analysis Populations

The PP population will serve as the primary population for the analysis of immunogenicity data in this study. The PP population consists of all randomized participants without deviations from the protocol that may substantially affect the results of the immunogenicity endpoint(s). Potential deviations that may result in the exclusion of a participant from the PP population for all immunogenicity analyses include:

- Failure to receive primary infant series vaccination (V114 or Prevnar 13TM Doses 1, 2, and 3) as per randomization schedule
- Receipt of prohibited medication or prohibited vaccine prior to the first study vaccination

Additional potential deviations that may result in the exclusion from the PP immunogenicity analyses at a particular timepoint include:

- Failure to receive Dose 4 of V114 or Prevnar 13TM according to vaccination schedule required at the timepoint for the analysis
- Failure to receive PentacelTM, VAQTATM, M-M-RTMII, VARIVAXTM, or HIBERIXTM according to vaccination schedule required at the timepoint for the analysis
- Failure to receive the scheduled doses of V114 or Prevnar 13TM (at least 28 days between Doses 1 and 2 and between Doses 2 and 3 [for PD3 and Predose 4 analysis], 12 months to 1 day prior to 16 months of age for Dose 4 [for PD4 analyses])
- Receipt of prohibited medication or prohibited vaccine prior to a blood sample collection
- Collection of blood sample at the timepoint for the analysis outside of the pre-specified window (as described in Section 1.3)

The final determination on protocol deviations, and thereby the composition of the PP population, will be made prior to the final unblinding of the database. Participants will be included in the vaccination group to which they are randomized for the analysis of immunogenicity data using the PP population.

A supportive analysis using the Full Analysis Set (FAS) population will also be performed for the primary immunogenicity endpoints and select secondary endpoints for the evaluation of concomitant vaccines. The FAS population consists of all randomized participants who received all study vaccinations required at the timepoint for the analysis and have serology result. Participants will be included in the vaccination group to which they are randomized for the analysis of immunogenicity data using the FAS population.

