Antigen-specific response rates for all antigens included in Pentacel TM	P	Miettinen and Nurminen	PP	Missing data will not	
at 30 days PD3	S	(estimate, 95% CI, p-value)	FAS	be imputed	
Antigen-specific GMCs for all	P	t-distribution with the variance estimate from a	PP	Missing data will not be imputed	
pertussis antigens included in Pentacel TM at 30 days PD3	S	linear model ‡ (estimate, 95% CI, p-value)	FAS		
Secondary Endpoints (H8)					
Anti-hepatitis A response rate at	P	Miettinen and Nurminen	PP	Missing data will not	
30 days PD4	S	(estimate, 95% CI, p-value)	FAS	be imputed	
Secondary Endpoints (H9)	T		1		
Antigen-specific response rates for all antigens included M-M-R TM II at	P	Miettinen and Nurminen	PP	Missing data will not	
30 days PD4	S	(estimate, 95% CI, p-value)	FAS	be imputed	

Endpoint/Variable (Description, Time Point)	Primary vs. Supportive Approach †	Statistical Method	Analysis Population	Missing Data Approach
Secondary Endpoints (H10)				
Anti-varicella response rate at 30	P	Miettinen and Nurminen	PP	Missing
days PD4	S	(estimate, 95% CI, p-value)	FAS	data will not be imputed
Secondary Endpoints (H11)				
Anti-PRP response rate at 30 days	P	Miettinen and Nurminen	PP	Missing
PD4	S	(estimate, 95% CI, p-value)	FAS	data will not be imputed
Secondary Endpoints (H12)				_
Proportion of participants with anti- PnPs serotype-specific IgG ≥0.35 µg/mL at 30 days PD3 for the 2 unique V114 serotypes	Р	Miettinen and Nurminen (estimate, 95% CI, p-value)	PP	Missing data will not be imputed
Secondary Endpoints (H13)				
Anti-PnPs serotype-specific IgG GMCs at 30 days PD3 for the 2 unique V114 serotypes	Р	t-distribution with the variance estimate from a linear model ‡ (estimate, 95% CI, p-value)	PP	Missing data will not be imputed
Secondary Endpoints (H14)				
Anti-PnPs serotype-specific IgG GMCs at 30 days PD4 for the 2 unique V114 serotypes	Р	t-distribution with the variance estimate from a linear model † (estimate, 95% CI, p-value)	PP	Missing data will not be imputed
Secondary Endpoints (H15)				
Proportion of participants with anti- PnPs serotype 3 IgG ≥0.35 μg/mL at 30 days PD3	P	Miettinen and Nurminen (estimate, 95% CI, p-value)	PP	Missing data will not be imputed
Secondary Endpoints (H16)				
Anti-PnPs serotype 3 IgG GMCs at 30 days PD3	P	t-distribution with the variance estimate from a linear model † (estimate, 95% CI, p-value)	PP	Missing data will not be imputed

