Secondary Endpoints (H17)				
Anti-PnPs serotype 3 IgG GMCs at 30 days PD4	P	t-distribution with the variance estimate from a linear model ‡	PP	Missing data will not

Endpoint/Variable (Description, Time Point)	Primary vs. Supportive Approach †	Statistical Method	Analysis Population	Missing Data Approach
---	--	--------------------	------------------------	-----------------------------

CI=confidence interval; FAS=full analysis set; GMC=geometric mean concentration; GMT=geometric mean titer; IgG=immunoglobulin G; OPA=opsonophagocytic activity; PD=postdose; PnPs=pneumococcal polysaccharide; PP=Per-Protocol; PRP=polyribosylribitol phosphate.

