# 9.9 Sample Size and Power Calculations

# 9.9.1 Sample Size and Power for Immunogenicity Analyses

The study will randomize participants in a 1:1 ratio to the 2 vaccination groups. The overall sample size will be approximately 1720 with 860 participants into each vaccination group. The sample size was chosen to ensure sufficient power for the multiple endpoints across both primary and secondary hypotheses.

With this study sample size and the assumptions listed below, the overall power for all the primary hypotheses is >95% to demonstrate non-inferiority of V114 to Prevnar 13TM for the 13 shared serotypes and the 2 unique serotypes for V114. The overall power for the secondary hypotheses for concomitant antigens evaluation is approximately 90%, to demonstrate superiority for the 2 unique V114 serotypes is >95%, and to demonstrate the superiority for the serotype 3 IgG response rates and IgG GMCs at 30 days PD3 is >95%, and IgG GMCs at 30 days PD4 is 94%.

The power for each individual hypothesis is provided below.

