## Secondary Immunogenicity Endpoints/Hypotheses (H15, H16, and H17)

This study has >95% power at a 1-sided 2.5% alpha-level to demonstrate that V114 is superior to Prevnar 13TM for serotype 3 based on the proportion of participants with anti-PnP serotype 3 IgG responses achieving the threshold value of 0.35 μg/mL at 30 days PD3. This power is calculated based on (1) 80% evaluability rate (688 evaluable participants per treatment group), (2) a superiority margin of 0 for the difference (V114 minus Prevnar 13TM), and (3) true response rates for serotype 3 as displayed in Table 11. These assumptions are based on the most current data available from the V114 program.

Table 11 Assumptions of the True Response Rates for V114 and Prevnar 13TM for Serotype 3 at 30 Days PD3

C	True Respo	onse Rate
Serotype	V114	Prevnar 13 TM
3	0.95	0.76

This study has >95% power at a 1-sided 2.5% alpha-level to demonstrate V114 is superior to Prevnar 13TM for serotype 3 based on the anti-PnP serotype 3 IgG GMCs at 30 days PD3 and 94% power based on the anti-PnP serotype 3 IgG GMCs at 30 days PD4. This power is calculated based on (1) evaluability rates of 80% at 30 days PD3 and 75% at 30 days PD4, (2) a superiority margin of 1.2 for the GMC ratio (V114/Prevnar 13TM), (3) true GMC ratios

V114-029-02 FINAL PROTOCOL 16-MAR-2021

of 1.94 at 30 days PD3 and 1.38 at 30 days PD4, and (4) the standard deviations of the natural log concentrations of 0.75 at 30 days PD3 and 0.73 at 30 days PD4. These assumptions are based on the most current data available from the V114 program.

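### Do the superiority hypotheses H12–H17 need a full-analysis-set result because they are tested only on the per-protocol population?

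*Combined protocol and SAP*

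**What the plan says.** Protocol Section 9.5.1 states: "The PP population will serve as the primary population for the analysis of immunogenicity data in this study". The FAS is supportive, and its scope is limited to analyses "for the primary immunogenicity endpoints and select secondary endpoints for the evaluation of concomitant vaccines". It is not an all-randomised set: "The FAS population consists of all randomized participants who received all study vaccinations required at the timepoint for the analysis and have serology result". Section 3.5.1 of the supplemental SAP keeps the same scope and asks for serology at the timepoint analysed.

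Table 6 in protocol Section 9.6.1 and Table 3 in the supplemental SAP follow this scope. H1–H11, all non-inferiority, each have a primary PP row and a supportive FAS row. H12–H17, all superiority, have one PP row. The serotype 3 entries "Anti-PnPs serotype 3 IgG GMCs at 30 days PD3" (H16) and "Anti-PnPs serotype 3 IgG GMCs at 30 days PD4" (H17) are examples. The missing-data entry throughout is "Missing data will not be imputed".

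For serotype 3 GMCs, Section 9.9.1 bases power on "evaluability rates of 80% at 30 days PD3 and 75% at 30 days PD4", a superiority margin of 1.2, true ratios of 1.94 (PD3) and 1.38 (PD4), and natural-log SDs of 0.75 and 0.73. It states 94% power for H17.

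**The concern.** In a non-inferiority comparison, analysing compliant participants is commonly the cautious choice, because deviations tend to make the arms look alike. In a superiority comparison the caution runs the other way: exclusions made after randomisation can enlarge an apparent benefit, and the wider set is the safer one. The plan supplies a second population where PP is already cautious and none where it is not. It gives no reason for this, and Amendment 02 added H15–H17 without widening the FAS scope.

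The planning figures make the omission look large: 20% of infants are expected not to be evaluable at PD3 and 25% at PD4. The hypothesis with least room is H17, where the assumed ratio of 1.38 sits close to the margin of 1.2. Section 9.8 requires H17 to succeed for the serotype 3 superiority objective to be met. The fear is a superiority claim made on PP that the wider set would not support.

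**Working it through.** **Inputs.** From Section 9.9.1: "The overall sample size will be approximately 1720 with 860 participants into each vaccination group"; evaluability 80% (PD3) and 75% (PD4); for H17, ratio 1.38, margin 1.2, SD 0.73, one-sided alpha 0.025. The documents give no FAS size, so the share added back and the ratio in those infants are assumptions below.

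**Planned numbers.** 860 × 0.80 = 688 and 860 × 0.75 = 645 per group. Per group, 172 (PD3) and 215 (PD4) are expected not to contribute.

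**Reproducing the H17 power.**
- SE = 0.73 × √(2/645) = 0.0407.
- Power = Φ(ln(1.38/1.2)/SE − 1.96) = Φ(0.1398/0.0407 − 1.96) = 93.0%, against 94% stated. An unrounded ratio near 1.385 would give 94.1%, so the stated figure is reproduced within rounding.
- Expected lower bound = 1.38 × exp(−1.96 × 0.0407) = 1.27.

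**What an FAS run of H17 could show.** Add back a fraction f of the 860, with true ratio r in those infants:
- n = 645 + 860f
- FAS ratio = exp[(645 ln 1.38 + 860f ln r)/n]
- SE and power as above, with the new n and ratio

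| f (n per group) | r = 1.0: ratio, lower bound, power | r = 1.2: power | r = 1.38: power |
|---|---|---|---|
| 5% (688) | 1.35, 1.25, 86% | 91% | 94% |
| 10% (731) | 1.33, 1.23, 76% | 90% | 96% |
| 15% (774) | 1.31, 1.22, 64% | 88% | 96% |

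The direction depends wholly on r. Even in the r = 1.0 column the expected lower bound stays above 1.2.

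**Is the serotype 3 FAS result missing?** Serotype 3 is one of the 13 shared serotypes, so it falls within H1 (PD3 response rate), H3 (PD3 GMC) and H5 (PD4 GMC). These are the same endpoints, arms and timepoints as H15, H16 and H17; only the margin differs. Table 6 gives H1, H3 and H5 an FAS row with estimate and 95% CI. Those intervals can be read directly against 0 and 1.2.

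**Is the 22F and 33F FAS result missing?** Yes. H2, H4 and H6 compare these serotypes with the lowest Prevnar 13 shared serotype (excluding serotype 3), not with the same serotype. But the distances to the margins are large:
- H12, extreme case (every omitted V114 infant a non-responder, every omitted Prevnar 13 infant a responder): 22F 0.95 × 0.8 − (0.02 × 0.8 + 0.2) = 0.544; 33F 0.90 × 0.8 − 0.216 = 0.504. The margin is 0.1.
- H14, if all the omitted 25% had ratio 1.0: 10^0.75 = 5.6. The margin is 2.0. H13 with 20% omitted: 10^0.8 = 6.3.

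**Who would the FAS add back?** Infants who missed a required dose or have no serology are outside both sets. What remains is mainly fully dosed infants with timing, prohibited-product or extra-dose deviations (Section 9.5.1; supplemental SAP Table 2). The 20–25% is planned non-evaluability and does not measure the gap between PP and FAS.

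**The case for a change.** The strongest case for a change is that nothing designates the H1, H3 and H5 FAS intervals as the check on H15–H17, and nothing says what happens if PP and FAS disagree. Infants with out-of-window draws or prohibited medication were vaccinated and bled, yet for H12–H17 their data enter no listed analysis. If they respond differently, H17 is where it would show, and extra rows would cost little. In the extreme case used above for H12, the H15 difference would also turn negative: 0.95 × 0.8 − (0.76 × 0.8 + 0.2) = −0.048.

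The textual part of this stands: the rows are absent and the asymmetry is unexplained. The rest carries less weight. The serotype 3 FAS numbers will be produced and reported whether or not a row is labelled H15–H17. The H15 extreme case concerns all omitted infants, including those without serology, whom this FAS cannot recover; with no difference at all in the omitted infants, the overall difference would still be 0.8 × 0.19 = 0.152. The absence of a rule for conflicting PP and FAS results applies equally to H1–H11.

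Making the FAS, or both sets, decisive would hold secondary hypotheses to a stricter rule than the primary ones. It would do so with a set that is itself conditional on dosing and serology after randomisation. That is a legitimate preference, but not the repair of an error.

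**Conclusion.** The observation about the tables is accurate, but no change is needed. The missing rows and the possible harm do not coincide. For serotype 3, where the result could be sensitive, the FAS estimates and intervals are already planned under H1, H3 and H5. For 22F and 33F, where the same-serotype FAS run is absent, the assumed effects are too far from the margins for it to matter.

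The size of the H17 concern rests on an assumed ratio of 1.0 in fully dosed infants, which the documents do not support. Across add-back shares of 5–15% and ratios of 1.0 to 1.38, FAS power runs from 64% to 96%, against 93% on PP.

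The choice of decision set is a fair trade-off, applied uniformly: all 17 hypotheses are decided on PP. PP membership is settled before final unblinding under in-house blinding, so exclusions cannot be chosen by known arm. H12, H13, H14, H16 and H17 must also clear margins beyond the null. Amendment 02 widened the Visit 3, 4 and 6 windows to bring more infants into PP, which should narrow the gap to the FAS. These conclusions assume effects near those in Section 9.9.1; the PP–FAS gap cannot be computed from the documents.
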